9.2 Calculation of the sample number

The sample size calculation is based on the 1-year primary endpoint. A value for the frequency of reaching the primary endpoint was placed around 60%, in accordance with the data reported in

Protocol number

NCT03521193

literature^{22, 27}. A sample of 92 patients was identified, necessary to obtain a potency of 80% able to detect as significant ($p < 0.01$, considering the Bonferroni correction for multiple tests) a correlation coefficient of 0.35 (adjusted for 4 confounding variables) between the variation of the migraine score sec. Anzola and any of the 5 factors (platelet reactivity, PGE1, PGE2, cytokines, serotonin) measured at baseline.

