8.4 Type and duration of subjects following adverse events

9. statistical analysis

9.1 statistical analysis

Continuous variables will be summarized using the DS \pm mean. Categorical variables are represented using frequencies and percentages. For the comparison between responders and non-responders, the Student's 2-code t-test or the Wilcoxon test for continuous variables will be used. The Chi-square test or the Fisher test will be used for categorical variables.

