9.3 Significance level to use

Statistical significance will be considered that obtained with a p value of 0.05.

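### Section 9.2 fixes Bonferroni at 0.01 for five factors. Holm's step-down at the same 5% overall error and N=92 would find more true markers if two or more exist.

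*Combined protocol and SAP*

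**What the plan says.** Section 9.2 is the only place where multiplicity is mentioned. It states "A sample of 92 patients was identified", "necessary to obtain a potency of 80% able to detect as significant" at p below 0.01, "considering the Bonferroni correction for multiple tests", "a correlation coefficient of 0.35 (adjusted for 4 confounding variables"), between the change in the Anzola score and "any of the 5 factors (platelet reactivity, PGE1, PGE2, cytokines, serotonin) measured at baseline". The 0.01 is 0.05/5. No stepwise method is named.

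Section 9.1 describes comparisons of responders with non-responders. It gives no multiplicity rule and does not list the correlation analysis on which 9.2 is sized.

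Section 9.3 reads "Statistical significance will be considered that obtained with a p value of 0.05". It does not say whether this is the level for each test or for the five tests together.

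**The concern.** A fixed level of 0.01 holds every factor to the strictest threshold, even after other factors have been declared significant. Holm's procedure relaxes the threshold after each rejection and keeps the same family-wise error, with no assumption on how the markers are correlated. For deciding which factors are significant, it can never do worse than Bonferroni.

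The study looks for predictive markers in the plural, and its rationale has vasoactive and inflammatory substances acting alongside platelet reactivity. If several of the five factors are truly related to the change in migraine score, a fixed 0.01 misses some that Holm would find in the same 92 patients.

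**Working it through.** **Inputs.** From 9.2: N=92, r=0.35, four covariates, five factors, 80% power, per-test level 0.05/5 = 0.01. The sidedness of the correlation test is not stated. Two-sided is assumed, because 9.1 uses "the Student's 2-code t-test or the Wilcoxon test for continuous variables will be used", which I read as two-tailed. The number of true factors and the correlation between factors are not given, so they are varied.

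**The plan's own figure.** Fisher's z gives N = ((z(0.995) + z(0.80)) / atanh(0.35))² + 3 + k, where k is the number of covariates charged.

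- k=0: ((2.576 + 0.842)/0.3654)² + 3 = 90.45, so 91. Power at N=92 is 80.8%.
- k=4: 94.45, so 95. Power at N=92 is 78.6%.
- A noncentral-t calculation gives 88; adding one patient per covariate gives 92.
- One-sided testing gives 79 (k=0) or 83 (k=4), which does not match.

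So 92 is reproduced closely enough, two-sided, with power of about 79% to 81% for one factor.

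**Holm's thresholds for five tests.** 0.05/5, 0.05/4, 0.05/3, 0.05/2 and 0.05/1, that is 0.01, 0.0125, 0.0167, 0.025 and 0.05, stopping at the first failure. For a single test at each of these levels, Fisher's z power at N=92 with k=4 is 78.6%, 80.8%, 83.5%, 87.0% and 92.1%. This is where any gain comes from.

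**Simulation.** 100,000 trials per scenario, effective n = 92 − 4 = 88, r=0.35 with the outcome for each true factor, independent factors. Each cell shows Bonferroni → Holm.

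| True factors | Power per true factor | At least one true factor found | All true factors found | Family-wise error |
|---|---|---|---|---|
| 0 | – | – | – | 4.9% → 4.9% |
| 1 | 79.0% → 79.1% | 79.0% → 79.1% | 79.0% → 79.1% | 3.9% → 4.6% |
| 2 | 78.9% → 80.8% | 96.0% → 96.0% | 61.8% → 65.6% | 2.9% → 4.5% |
| 3 | 79.0% → 83.0% | 99.4% → 99.4% | 48.1% → 58.1% | 2.1% → 4.3% |
| 4 | 79.0% → 86.0% | 99.9% → 99.9% | 37.2% → 57.0% | 1.0% → 3.8% |
| 5 | 78.9% → 90.0% | 100% → 100% | 28.0% → 64.0% | none possible |

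**Correlated factors, all five true.** With inter-correlation 0.3, power per factor is 79% → 89% and the chance of finding all five about 40% → 70%. With 0.5, the figures are 79% → 88% and 48% → 74%.

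**Size of the family.** Section 6.1 measures three cytokines (IL-1, IL-6, TNF-alpha) and many platelet readouts. Counting the cytokines as three and platelet reactivity as one gives 4 + 3 = 7 tests. Seven independent tests at 0.01 have a family-wise error of 1 − 0.99⁷ = 6.8%. A seven-test Holm family would start at 0.05/7 = 0.0071. There the same Fisher's z formula gives power at N=92 of 75.1% (k=4) to 77.6% (k=0) for one factor, against 78.6% to 80.8% at 0.01.

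**The case against.** The case for leaving the plan alone is fair, and much of it stands.

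- **Bonferroni is valid.** A reader might infer that 9.2 contains an error or that 92 patients are too few because of it. The documents do not support that: the level of 0.01 is correct for five tests and N is reproduced.
- **The design target does not move.** Section 9.2 powers one factor at a time, and Holm's first step is the same 0.01. With one true factor the gain is 0.1 point, and the chance of finding at least one true marker is essentially the same. Nobody should infer that Holm allows fewer patients.
- **The number of true markers is unknown.** The rationale says that the substances may act together with platelet reactivity. It does not say that several baseline factors each correlate at 0.35 with outcome, so Holm cannot be said to find more markers unconditionally.
- **28% to 64% is a best case.** Five independent factors at r=0.35 would explain 5 × 0.35² = 61% of the covariate-adjusted variance in the change in score, which is very favourable.
- **Bonferroni is tied only to the sample size.** That the analysis itself will use it is an inference from 9.2. Equally, a reader might take 9.3 to mean five uncorrected tests at 0.05, with a family-wise error of 1 − 0.95⁵ = 22.6% if independent. The text does not establish that either; 0.05 may be the overall level.
- **Holm has a price.** It spends more of the allowed error (4.6% against 3.9% with one true factor, still within 5%), and simultaneous confidence intervals are less direct.

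None of this removes the point that, for the same patients and the same 5% limit, Holm never rejects fewer factors and rejects more when several are real.

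**Conclusion.** The point holds as a cheap improvement. Under the working's assumptions the gain in power per true factor is negligible with one true factor, about 2 points with two, 4 with three, 7 with four and 11 with five. Correlation between the markers reduces it slightly: about 10 points with five true factors at inter-correlation 0.3.

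That Holm rejects at least as much as Bonferroni at the same family-wise error needs no assumption. The sizes rest on r=0.35 from 9.2 applying to every true factor, and on assumed two-sided tests, number of true factors and marker correlation. The 5% limit holds for either method only if the family is exactly the five tests counted in 9.2, which the list of assays does not yet secure.

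**What to change.** - In 9.1, add the adjusted correlation analysis and state that the five baseline factors are tested by Holm's procedure at overall two-sided 0.05: order the five p values, compare them with 0.01, 0.0125, 0.0167, 0.025 and 0.05, and stop at the first failure.
- In 9.3, say that 0.05 is the family-wise level for these five tests. This reconciles it with the 0.01 in 9.2.
- In 9.2, replace the reference to Bonferroni by Holm. Keep N=92 and the 0.01 first step as the sizing basis.
- Name one pre-specified variable for each factor, in particular for cytokines and platelet reactivity. Otherwise enlarge the Holm family to the actual number of tests; the 0.01 first step and the stated 80% power then no longer apply as written and must be recalculated.

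The cost is a few sentences and the choice of one variable per factor, made before the marker data are related to outcome. No patients or measurements are added. If simultaneous intervals are wanted, 99% intervals for each of five correlations remain valid, but may include zero for a factor that Holm rejects at a later step; the plan should say so.

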5.0 Characteristics of the population

The study population includes patients with patent foramen ovale and previous neurological event (TIA or stroke) with clinical indication to the percutaneous correction of the defect according to guidelines or in a previous TIA/stroke absence when addressed to the pfo treatment for migraine non responsive to specific therapy, as per the evaluation of the neurologist specialist. Similar evaluations are not currently available in the literature able to identify patients who, not responsive to specific drug therapy, as prescribed by the neurologist specialist, and carriers of PFO, can be directed to the percutaneous correction of the defect with indication at the moment "off-label" with respect to what is codified by the international guidelines (ESC and AHA / ACC) but potentially effective in the control of symptomatology. The advantage of PFO correction observed so far only in patients undergoing PFO correction as a result of cerebral ischemic events, could translate into migraine workers in a reduction in costs borne by the National Health System in the number of neurological medical examinations, pharmacological prescriptions and missed working days.

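### Adjustment for baseline Anzola score is not assured, so a marker that only reflects migraine severity at entry can appear to predict response to closure

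*Combined protocol and SAP*

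**What the plan says.** Section 9.2 bases the sample size on "a correlation coefficient of 0.35 (adjusted for 4 confounding variables") "between the variation of the migraine score sec. Anzola and any of the 5 factors" measured at baseline. The 4 confounders are not identified there or elsewhere, and the section does not say whether the variation is absolute or percent. Section 4.1 words the primary outcome differently, as a percentage regression of episodes with aura.

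The only analysis text is section 9.1: "For the comparison between responders and non-responders, the Student's 2-code t-test or the Wilcoxon test for continuous variables will be used", with chi-square or Fisher tests for categorical data. It contains no regression and no covariates, and it does not define a responder.

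Section 5.0 describes two entry routes. One is a previous TIA or stroke with a guideline indication for closure. The other is entry "in a previous TIA/stroke absence when addressed to the pfo treatment for migraine non responsive to specific therapy". Section 5.1 neither requires migraine nor sets a minimum Anzola score, although section 6.1 frames the hypothesis around patients with migraine symptoms. Under section 6.1 the score is taken before closure and again at 6 and 12 months, and the items shown in Table 1 start at 0.

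**The concern.** A change score contains the baseline score. Patients who start high have room to fall and tend to fall partly through ordinary fluctuation. Patients who start near zero can hardly fall. Anything correlated with the starting score then tends to correlate with the fall, even if it carries no further information about outcome. Two entry routes with no severity threshold allow a wide spread of starting scores. The study's own hypothesis, that platelet reactivity and vasoactive substances contribute to the onset and maintenance of migraine, makes a marker-severity correlation plausible.

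The stake is the study's main conclusion. Section 4.1 seeks markers that predict benefit from closure, and section 5.0 explains that such findings could help identify drug-refractory patients for closure outside current guideline indications. A proxy for entry severity reported as a response predictor would mislead that use.

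**Working it through.** **1. The plan's own figure.** Inputs from section 9.2: r = 0.35, power 80%, alpha 0.01 (0.05/5, "considering the Bonferroni correction for multiple tests"), 4 covariates, N = 92. Two-sided testing is assumed, in line with the two-tailed t-test of section 9.1.

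Fisher z: n = ((2.576 + 0.842)/atanh 0.35)² + 3 + k, with atanh 0.35 = 0.3654.
- k = 0: 90.45, so 91.
- k = 4: 94.45, so 95. Power at N = 92 is 78.6%.
- With a t critical value and bias correction, k = 4 gives 94, with power 78.9% at 92.

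The stated 92 is reproduced within about 2 patients or 2 points of power. The sample size is not in question.

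**2. Correlation induced by baseline.** Let B be the baseline score, F the 12-month score and D = B − F the fall. Assume equal SDs, corr(B, F) = b, and a marker with correlation ρ with B that is unrelated to F once B is known. None of these values is in the documents.

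- With SD = 1: Var(D) = 2(1 − b) and Cov(B, D) = 1 − b.
- corr(B, D) = (1 − b)/√(2(1 − b)) = √((1 − b)/2).
- Induced corr(marker, D) = ρ√((1 − b)/2).

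**3. Chance that such a marker is declared significant.** For N = 92, 4 irrelevant covariates and two-sided p < 0.01, this is approximately Φ(atanh(r)·√(92 − 3 − 4) − 2.576). Example: b = 0.5 and ρ = 0.5 give r = 0.25, so 0.2554 × 9.220 = 2.355 and Φ(−0.221) = 41%.

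| b | ρ = 0.3 | ρ = 0.4 | ρ = 0.5 |
|---|---|---|---|
| 0.3 | r = 0.18, 18% | r = 0.24, 36% | r = 0.30, 59% |
| 0.5 | r = 0.15, 12% | r = 0.20, 24% | r = 0.25, 41% |
| 0.7 | r = 0.12, 7% | r = 0.15, 13% | r = 0.19, 22% |

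Simulation of 6,000 studies per cell agrees, giving 6.5% to 58.5% across the table. With baseline score as one of the 4 covariates, the simulated rate is 0.8% to 1.2% in every cell.

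**4. Responder comparison.** If a responder is defined as one of the 60% with the largest absolute falls (an assumption; section 9.2 places the endpoint frequency at about 60%), the unadjusted t-test at the 0.05 level of section 9.3 rejects in about 21%, 32% and 47% of studies at b = 0.5 and ρ = 0.3, 0.4 and 0.5. The nominal rate is 5%.

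**5. Percent change.** Results depend heavily on the response model. They run from about the nominal 1% (proportional response drawn independently of the marker) to 7%, 14% and 22% (an assumed bounded 0-10 score, b = 0.5, ρ = 0.3, 0.4 and 0.5). In the latter setting the rates for absolute change were 12%, 24% and 40%.

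**6. The opposite case.** Suppose the marker tracks stable severity and the single baseline score is that severity plus noise. At b = 0.5 and ρ = 0.3, 0.4 and 0.5, the change score rejects in about 1% of studies, while the 12-month score adjusted for baseline rejects in 19%, 43% and 74%.

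**The case against.** A reader might infer that the plan omits baseline adjustment. The documents do not support that. Section 9.2 provides for 4 confounders, and because they are unnamed, baseline score is neither included nor excluded. What stands against the plan is that those confounders appear only in the sample-size paragraph, and section 9.1 contains no model for them to enter.

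A reader might also infer that the outcome is raw change and that a severity marker will be declared a predictor. Neither is documented. Section 9.2 leaves the form of the variation open, section 4.1 speaks of percentage regression, and percent change inflates the error less. Section 5.0 gives no severity for either route, and no marker-severity correlation is reported. If response, as defined, were independent of baseline, the responder test would keep its nominal error rate. The problem can arise; it is not shown that it must.

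The strongest point is step 6. If the marker reflects stable severity, the change score behaves well and the baseline-adjusted analysis finds an association. This is Lord's paradox, and it rules out any guarantee that adjustment restores a 1% error rate. It does not overturn the recommendation. In that case the marker truly adds information about the 12-month score beyond the observed baseline, which is the predictive question section 4.1 asks. It does restrict what the adjusted result means.

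**Conclusion.** The concern holds as a gap in specification with a potentially material effect. Adjustment for baseline Anzola score is not assured, and the only stated analysis is unadjusted. For absolute change at p < 0.01, a marker that only reflects entry severity would be declared predictive in about 6% to 60% of studies of 92, against 1%. This rests on equal variances, b from 0.3 to 0.7, ρ from 0.3 to 0.5, and no link between marker and 12-month score given baseline. Percent change reduces the excess and in some models removes it.

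The adjusted analysis answers whether the marker predicts the 12-month score given the observed baseline. The design in section 4.2 is single-centre and observational, with no untreated group described, so neither analysis can separate benefit of closure from natural course.

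**What to change.** - Add to section 9.1 a regression of the 12-month Anzola score on each of the 5 markers, with baseline Anzola score as a covariate and entry route (stroke/TIA or refractory migraine) as another of the 4 confounders. Name the remaining two.
- Define the variation in section 9.2 as absolute or percent, and define a responder.
- Label the unadjusted responder comparison as descriptive.
- Report the change-score result as a sensitivity analysis, with a sentence explaining why it may disagree with the adjusted result when the single baseline score is noisy.
- State that, without an untreated group, a marker of natural course cannot be distinguished from a marker of benefit from closure.

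Cost: wording only. The baseline score is already collected (section 6.1) and the entry route is known at referral (section 5.0). Both fit within the 4 confounders already counted, so N = 92 stands. If baseline score were instead a fifth covariate, Fisher z gives 95.45, so 96 rather than 95: one more patient, or power at 92 of 78.0% rather than 78.6%.

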9.3 Significance level to use

Statistical significance will be considered that obtained with a p value of 0.05.

9.4 Criteria for the conclusion of the trial

9.5 Steps to handle missing, unused, or spurious data

10. Direct access to original data and documents

The investigator will allow monitoring, verification, review by the Ethics Committee or any other control body, allowing direct access to the original data and documents.

11. Quality Control and Assurance Procedures

Regular internal monitoring visits will be carried out.

12. Ethical Aspects

The Study will be conducted in full respect of human dignity and its fundamental rights as dictated by the "Treaty of Helsinki" and subsequent amendments, by the "Good Clinical Practice" (GCP) rules issued by the European Community and in accordance with all local laws and regulations concerning clinical trials.

13. Data retention and analysis

Sensitive data, managed on computer support, will be processed as per current legislation and therefore the personal information will be separated from those that determine a clinical picture of the patient. The original data will be kept for 7 years by the investigators and, on request, made public. The reference that links the clinical data to a patient will be kept in a Microsoft Excel format file on the personal computer of the project coordinator. The patient's personal data are not of interest for the trial in question.

14. Privacy

The researcher undertakes to obtain and record on paper or computer and in a clear manner the information required in this protocol and to ensure safe storage and confidential access to information. The patient's surname(s), first name(s) and date of birth will only be present in the source document (medical record). Each biological information or material will be identified with a unique code that will allow to associate the clinical data with the laboratory results but, in no case, with the identity of the patient.

15. Insurance

For the risks deriving from participation in the study, the Monzino Cardiology Center, IRCCS has an adequate insurance coverage stipulated in accordance with the laws in force on the subject. By contract, the insurance will respond only in cases where the damage suffered by the patient is related to any procedure associated with his participation in the study. The insurance will not

Protocol number

NCT03521193

reimburse damages resulting from procedures conducted by the patient not covered by this Protocol.

16. Publication criteria

The results of the study will be used by the investigators only within the objectives indicated in the protocol.

17. Intellectual property

All publications and /or communications related to the study will be previously approved by the P.I. of the Institution involved and in particular by the PI [name] of the Monzino Cardiology Center.

The product of data processing in connection with this Study, including documentation, information, materials and results in any form generated in the course of the study, will be the property of the investigators.

18. Administrative requirements

Beginning of the study

The study will begin only after the written approval of the Ethics Committee.

Standards of Good Clinical Practice and European Directives for Clinical Trials

The investigators assure that the study will be conducted in accordance with the Helsinki Declaration (1964), Amendment of Somerset West, South Africa (1996) and with the international standards of standards of Good Clinical Practice, of the ICH (International Conference on Harmonization) and in accordance with all local laws and regulations concerning clinical trials. The study will not begin until there is approval, by the Ethics Committee, of the protocol, the information sheet for the subjects, the consent procedure and the written informed consent form.

Amendments to the Protocol

Any proposed amendment will only be implemented if approved by the Ethics Committee

confidentiality

The investigators involved are committed to preserving the confidentiality of the patients taking part in the study.

responsibility

The person responsible for the processing of the personal data of the participants in this study is [REDACTED]

The scientific manager of this study [REDACTED]

The statistical manager of this study is [REDACTED]

Conflict of interest

Researchers involved in this project declare the absence of conflicts of interest.

19 Selected bibliography

1. Headache Classification Subcommittee of the International Headache Society. The International Classification of Headache Disorders: II edition. *Cephalalgia*. 2004;24:9–160.
4. Rigatelli G. Migraine and patent foramen ovale: connecting flight or one-way ticket? *Expert Rev Neurother*. 2008;8:1331–1337.
